Table 5 Schedule of Procedures/Assessments in Study E2609-G000-301 (Revised per Amendments 05 and 06)

Phase Period	Randomization														ED ^b	Follow-Up		UNS Visit ^d
	Treatment												14 ^c	15 ^c				
Visit ^a	2	3	4	5	6	7	8	9	10	11	12	13						
Day	1	15	29	57	85	183	274	365	456	547	638	729		757	813			
Week	1	3	5	9	13	27	40	53	66	79	92	105		109	117			
Weeks elapsed since 1st dose	0	2	4	8	12	26	39	52	65	78	91	104		108	116			
Nominal months elapsed since 1st dose	0		1	2	3	6	9	12	15	18	21	24		25	27			
Procedures/ Assessments																		

should be conducted within the 7 days before Visits 9 and 13. In the event of an Unscheduled Visit, the investigator in consultation with the medical monitor will determine whether or not a safety MRI should be conducted. If an ED Visit takes place, an MRI is to be conducted if not already performed during the preceding 90 days.

- t: Amyloid PET scanning (if subject has consented to optional substudy) will be performed with a locally approved amyloid β imaging agent (eg, Neuraceq, if available) or an agent under clinical investigation if no agents are approved locally; the imaging agent must remain unchanged for an individual subject throughout the study. An amyloid PET scan will only be performed at an ED Visit if the subject has been treated with study drug for at least 39 weeks and at least 6 months has elapsed since the prior amyloid PET scan was performed. (revised per Amendments 04 and 05)
- u: For subjects who consent to the tau PET longitudinal substudy, tau PET will be conducted at 24 months of treatment during the Core Study (or at the ED Visit, provided the subject has received at least 39 weeks of study drug). At the 24 month timepoint (or at the ED Visit), the amyloid and tau PET scans can be performed in either order but must be at least 48 hours apart. If the subject has also consented to the longitudinal CSF substudy, the longitudinal substudy assessments can be performed in any order, with at least 48 hours between each procedure. Tau PET scanning will be performed using a sponsor-supplied tau PET imaging agent, eg PI-2620. (revised per Amendment 05)
- v: Site staff will contact the subject or the study partner the day before the PK blood sampling to provide instructions that subjects must not take their study drug at home on the day of the PK blood sampling. During this telephone contact with the subject or the study partner, the site staff should document the time that the subject took their study drug that day, ie, the day before the PK blood sampling.
- w: Two plasma PK samples will be obtained: 1 sample at predose (trough) and another sample 1 to 6 hours postdose at Visits 3, 4, 6, 7, 9, and 11 and another sample 4 to 8 hours postdose at Visit 13 (or ED). Therefore, subjects or their study partners must be instructed not to take their study drug at home on the day the PK sampling is performed. Instead, subjects will take the study drug at the clinic after collection of the predose PK sample. At Visit 13 (or ED), the PK blood sample should be collected shortly before or after completing the LP for subjects participating in the CSF substudy. If the study drug is temporarily suspended, postdose PK samples will not be required. If at an ED Visit, the subject has already stopped study drug, then postdose PK samples are not required.
- x: PD and exploratory biomarker blood samples should be collected at fasting or at least 2 hours after the most recent meal and, as far as is feasible, samples should be taken at the same time of day at all visits. Samples should be taken predose at Visits 2, 3, 4, 6, 7, 9, 11, 13 (or ED), 14, and 15. (revised per Amendments 01, 03, and 04)
- y: For subjects who consent to participate in the CSF longitudinal substudy. Visit 13 (or ED) also includes blood PK and PD assessments and so the subject will be dosed at the clinic on these days. A CSF sample will be collected by LP between 4 and 8 hours postdose and at the same time of day as the subject's Screening LP (±1 hour). The CSF sample will be taken with the subject fasting (preferred) or at least 2 hours after the most recent meal. A gravity drip collection method must be used. If performed on the same day as the cognitive tests, the LP will be performed after the cognitive tests; the subject should rest and drink some fluid to hydrate after the cognitive tests and before the LP. Subjects will be encouraged to stay at the site after completion of LP for medical observation. The CSF sample will not be taken at the ED Visit if this visit occurs within 39 weeks of treatment or 3 months of a previous CSF sample. If at an ED Visit, the subject has already stopped study drug, then no dosing will take place, but the CSF sample will still be collected unless it was already collected within the past 3 months. Subjects receiving concomitant anticoagulation/antiplatelet therapy should have prothrombin time and INR (derived from prothrombin time) before LP; if they are assessed by the investigator to be at risk for bleeding, they are to be excluded from CSF collection. Note that subjects who are assessed by both amyloid PET and CSF are required to wait for a minimum of 48 hours between the 2 procedures. (revised per Amendments 01, 02, and 04)
- z: Subjects reporting AEs relating to abnormal dreams, nightmares, or sleep terror will be questioned on the nature, frequency, and impact of these events.
- aa: AEs that may signal drug abuse potential require a more detailed follow-up through completion of a specific eCRF form (Possible drug abuse potential form/questionnaire). Similarly, AEs

Table 5 Schedule of Procedures/Assessments in Study E2609-G000-301 (Revised per Amendments 05 and 06)

Phase Period	Randomization													Follow-Up			UNS Visit ^d
	Treatment												ED ^b	14 ^c	15 ^c		
Visit ^a	2	3	4	5	6	7	8	9	10	11	12	13					
Day	1	15	29	57	85	183	274	365	456	547	638	729		757	813		
Week	1	3	5	9	13	27	40	53	66	79	92	105		109	117		
Weeks elapsed since 1st dose	0	2	4	8	12	26	39	52	65	78	91	104		108	116		
Nominal months elapsed since 1st dose	0		1	2	3	6	9	12	15	18	21	24		25	27		
Procedures/ Assessments																	

reported during the first 4 weeks following the last dose of study drug that might indicate physical dependency also require a more detailed follow-up through completion of the same eCRF form. Categories and examples of AEs indicating signals of possible drug abuse are provided in [Appendix 3](#) and a more comprehensive list is provided in the eCRF Completion Guidelines. (revised per Amendments 02 and 04)

- bb: The first dose of study drug will be given to the subject at the study site. Subjects will be encouraged to stay at the site for observation for at least 30 minutes following their first dose of study drug. The duration of this observation period can be extended at the investigator’s discretion, eg, if warranted by medical history or concomitant medication. (revised per Amendment 04) Visit 2 bottles are re-dispensed at Visit 3 after accountability is performed. (revised per Amendment 06)
- cc: Only for Extension Phase subjects who did not participate in optional longitudinal substudies in the Core Study but who wish to consent to optional longitudinal substudies in the Extension Phase
- dd: For subjects entering the Extension Phase only
- ee: Immunological assessments only required for subjects randomized before 07 Sep 2018
- ff: New AEs will be collected for 4 weeks post last dose and followed-up for 12 weeks, or until resolution, whichever comes first. If >4 weeks post last dose, AEs relating to study procedures will be collected only
- gg: C-SSRS to be completed if any positive responses from the Clinical Assessment of Suicidal Thinking and Behavior
- hh: For those subjects entering the Extension Phase, NPI-12 will be used if available and both NPI-10 and NPI-12 scores calculated.
- ii: Not required for those entering Extension Phase

9.5.2.2 Description of Procedures/Assessments Schedule

Please refer to [Table 4](#) and [Table 5](#) for the timings of the procedures and assessments to be performed during the study. Screening assessments will be organized into 5 tiers (see [Table 4](#)). See [Section 9.5.1](#) for a full description of the procedures and assessments to be performed during this study.

[Table 6](#) presents the number of blood and CSF samples, and the estimated total volume of blood and CSF that will be collected throughout the study. (revised per Amendment 03) Additional samples may be taken at the discretion of the investigator if the results of any tests fall outside reference ranges or if clinical symptoms necessitate testing to ensure subject safety. Actual specimen volumes may vary based on local regulations. (revised per Amendment 03)

Table 6 Summary of Estimated Blood and CSF Sample Volumes

Assessment	Total Number of Collection Time Points	Sample Volume, Number of Time Points × Volume per Collection (mL)			Total Volume ^a (mL)
		Screening Visits	Visit 2 Baseline (predose) (revised per Amendment 04)	Treatment and Follow-Up Periods	
Blood					
Clinical chemistry (revised per Amendments 03 and 04)	15	1×2.5 mL	1×2.5 mL	13×2.5 mL	37.5 mL
Serum pregnancy test at Screening (females of child-bearing potential only)	0	can use blood drawn for clinical chemistry	can use blood drawn for clinical chemistry	none	no additional volume
Hematology (revised per Amendment 04)	15	1×2 mL	1×2 mL	13×2 mL	30 mL
Coagulation (revised per Amendments 03 and 04)	15	1×1.8 mL	1×1.8 mL	13×1.8 mL	27 mL
Thyroid function tests (thyroid stimulating hormone, free triiodothyronine and free thyroxine)	1	1×5 mL	none	none	5 mL
Viral screen at Screening (Hepatitis B and C) (revised per Amendment 03)	1	1×2.5 mL	none	none	2.5 mL
Viral characterization at Visit 2 (previous exposure to CMV, HSV1, HSV2, etc.) (revised per Amendments 03 and 04)	1	None	1×3.5 mL	none	3.5 mL

Table 6 Summary of Estimated Blood and CSF Sample Volumes

Assessment	Total Number of Collection Time Points	Sample Volume, Number of Time Points × Volume per Collection (mL)			Total Volume ^a (mL)
		Screening Visits	Visit 2 Baseline (predose) (revised per Amendment 04)	Treatment and Follow-Up Periods	
Vitamin B12 at Screening and MMA where available (revised per Amendments 03, 04, and 06)	0	can use blood drawn for TFT	none	none	no additional volume
Blood for immunologic assessments Amendments 01, 04, and 06 ^b	8	none	1×10 mL	7×10 mL	80 mL
Blood for PBMCs (revised per Amendment 06)	4	none	1×10 mL	3×10 mL	40 mL
Blood for immune status (revised per Amendment 04)	8	none	1×5 mL	7×5 mL	40 mL
AD diagnostics and exploratory biomarker (revised per Amendment 04)	1	1×6 mL	none	none	6 mL
PD and exploratory biomarker sample (revised per Amendments 02, 03 and 04)	10	none	1×12 mL	9×6 mL	66 mL
PK analysis (revised per Amendments 02 and 03)	7	none	none	14×2 mL	28 mL
Pharmacogenomic sample (revised per Amendment 03)	1	1×6 mL	none	none	6 mL
All blood samples, total volume collected (revised per Amendments 02, 03, 04, and 06)		25.8 mL	46.8 mL	298.9mL	371.5 mL
CSF					
Amyloid eligibility	1	1×12 mL	none	none	12 mL
PD / PK (optional longitudinal substudy)	1	none	none	1×12 mL	12 mL

Note: Actual volumes may be less, based on regional differences in Central Laboratories.

AD = Alzheimer's disease, CMV = cytomegalovirus, CSF = cerebrospinal fluid, HSV1 = herpes simplex virus 1 (orolabial herpes), HSV2 = herpes simplex virus 2 (genital herpes), PBMCs = peripheral blood mononuclear cells, PD = pharmacodynamics, PK = pharmacokinetic, TFT = thyroid function Test.

a: The total volume includes all blood/CSF collection from Screening through Week 117 (Follow-up Visit); actual volume may vary based on local regulations. (revised per Amendment 03)

b: Immunological assessment samples not required for subjects randomized after 07 Sep 2018 - reducing total blood volume to 291.5 mL (revised per Amendment 06)

9.5.3 Appropriateness of Measurements

All clinical assessments are standard measurements commonly used in studies of AD.

Standard safety assessments incorporated into this protocol include assessment of AEs and SAEs, measurement of vital signs, clinical laboratory assessments, physical examinations (including dermatologic review), neurologic examinations, ECG measurements, assessments of suicidal thinking and behavior, and MRI.

9.5.4 Reporting of Serious Adverse Events, Pregnancy, and Events Associated with Special Situations

9.5.4.1 Reporting of Serious Adverse Events

All SAEs, regardless of their relationship to study treatment, must be reported on a completed SAE form by email or fax as soon as possible but no later than 24 hours from when the investigator becomes aware of the event.

SAEs, regardless of causality assessment, must be collected up to 4 weeks after the last dose of study drug. All SAEs must be followed to resolution or, if resolution is unlikely, to stabilization. Any SAE judged by the investigator to be related to the study treatment or any protocol-required procedure should be reported to the sponsor regardless of the length of time that has passed since study completion. (revised per Amendment 06)

The detailed contact information for reporting of SAEs is provided in the Investigator Study File.

For urgent safety issues, please ensure all appropriate medical care is administered to the subject and contact the appropriate study team member listed in the Investigator Study File.

It is very important that the SAE report form be filled out as completely as possible at the time of the initial report. This includes the investigator's assessment of causality.

Any follow-up information received on SAEs should be forwarded within 1 business day of its receipt. If the follow-up information changes the investigator's assessment of causality, this should also be noted on the follow-up SAE form.

Preliminary SAE reports should be followed as soon as possible by detailed descriptions including copies of hospital case reports, autopsy reports, and other documents requested by the sponsor.

The investigator must notify his/her IRB/IEC of the occurrence of the SAE in writing, if required by their institution. A copy of this communication must be forwarded to the sponsor, or its designee, to be filed in the sponsor's Trial Master File.

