All subjects in the Core Study who discontinue study drug before reaching 12 months of treatment will also be asked to return to the clinic for a 12-month clinical assessment and then again at 24 months. Subjects who discontinue treatment between 12 and 24 months of treatment will be asked to return to the clinic for a 24-month clinical assessment. Subjects who discontinue early from study drug are considered “on study” as long as they continue to return for their regularly scheduled clinical assessments at 12 and 24 months as outlined above, at which efficacy and quality of life will be assessed along with concomitant medications. New AEs will be collected for 4 weeks post last dose and followed up for 12 weeks, or until resolution, whichever comes first. AEs relating to study procedures will be collected until the end of study participation. (revised per Amendment 06) However, subjects who discontinue study drug early are not considered to have ‘completed’ the study as a final Subject Disposition.

The primary reason for discontinuation and all other reason(s) contributing to the subject’s discontinuation from study drug(s) should be collected on the ED from study drug eCRF page. In addition, the date of last dose of study drug(s) will be recorded on the Study Drug Dosing eCRF page. If a subject discontinues study treatment and the study at the same time, the end-of-study procedures (Final Visit) will be followed (see [Section 9.5.5](#)).

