- a: A window of ±3 days will be permitted for Visits 3 and 4. A window of ±7 days will be permitted for Visits 5 and 6. A window of ±10 days will be permitted for Visits 7 to 13 inclusive (including for subjects who discontinue study drug early but who return for clinical assessments at 12 and 24 months). These windows should be calculated from Day 1. A window of ±3 days calculated from the last dose will be permitted for the Follow-up Visits. If use is made of the permitted visit windows, every effort should be made to bring the subject back in line with the “weeks elapsed since 1st dose” at subsequent visits.
- b: Subjects who discontinue taking study drug prematurely for any reason will undergo an ED Visit within 7 days of their last dose of study drug. In addition, Follow-up Visits will be scheduled 4 and 12 weeks after the last dose of study drug (Visit 14 and Visit 15, respectively). Subjects who discontinue study drug before reaching 12 months of treatment will also be asked to return to the clinic for a 12 month clinical assessment and then again at 24 months. Subjects who discontinue treatment between 12 and 24 months of treatment will be asked to return to the clinic for a 24 month clinical assessment. Subjects who discontinue early from study drug are considered “on study” as long as they continue to return for their clinical assessments at 12 and 24 months as outlined above, at which efficacy (MMSE, CDR, ADAS-cog14) and quality of life (EQ-5D, QOL-AD and Zarit’s Burden Interview) will be assessed along with concomitant medications. New AEs will be collected for 4 weeks post last dose and followed up for 12 weeks, or until resolution, whichever comes first. If >4 weeks post last dose, only AEs relating to study procedures will be collected. These 12 and 24 month clinical assessment visits do not need to be attended if they fall within 8 days (visit window) after the ED Visit or within ±8 days of either of the Follow-up Visits (Visit 14 and Visit 15).

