9.5.5 Completion/Discontinuation of Subjects

A subject may elect to withdraw from the study at any time for any reason. All subjects who discontinue study drug early for any reason will undergo an ED Visit within 7 days of their last dose of study drug (see [Section 9.1.2.2](#)). In addition, Follow-Up Visits will be scheduled 4 and 12 weeks after the last dose of study drug (Visit 14 and Visit 15, respectively) (see [Section 9.1.2.2](#)). These Follow-up Visits will be conducted to monitor efficacy and safety parameters after early withdrawal from the study or discontinuation of study drug. See [Table 5](#) for full details of the assessments to be performed at these visits.

All subjects who discontinue study drug before reaching 12 months of treatment will also be asked to return to the clinic for a 12 month clinical assessment and then again at 24 months. Subjects who discontinued treatment between 12 and 24 months of treatment will be asked to return to the clinic for a 24-month clinical assessment. Subjects who discontinue early from study drug are considered “on study” as long as they continue to return for their clinical assessments at 12 and 24 months as outlined above, at which efficacy and quality of life will be assessed along with concomitant medications and AEs. However, subjects who discontinue study drug early are not considered to have ‘completed’ the study as a final Subject Disposition. A subject removed from the study for any reason may not be replaced.

The investigator will promptly explain to the subject involved that the study will be discontinued for that subject and provide appropriate medical treatment and other necessary measures for the subject. A subject who has ceased to return for visits will be followed up by mail, phone, or other means to gather information such as the reason for failure to return, the status of treatment compliance, the presence or absence of AEs, and clinical courses of signs and symptoms.

The primary reasons for early withdrawal from the study are: AE, lost to follow-up, subject choice, withdrawal of consent, pregnancy, study terminated by sponsor, and other. The secondary reasons for early withdrawal from the study are: AE, subject choice, and other.

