Safety analysis will be performed similarly to analyses in the Core Study. The Core Study baseline will be used for subjects who are randomized to elenbecestat initially, the Extension Phase baseline will be used for subjects who are randomized to placebo but receive elenbecestat during the Extension Phase. The incidence of AEs (including changes from baseline in physical and neurological examinations, and dermatological assessments), out-of-normal-range laboratory safety test variables, abnormal ECG findings, out-of-range vital signs, suicidality (C-SSRS), and changes from baseline in laboratory safety test variables, ECGs, safety MRI, vital sign measurements will be summarized by using descriptive statistics.

Efficacy Analyses

The following efficacy endpoints will be summarized by descriptive statistics and graphs:

- Changes from baseline in CDR-SB, ADCOMS, MMSE, FAQ, ADAS-cog14, and ADAS-cog14 Word List (immediate recall and delayed recall)
- Time to conversion to dementia for subjects who were not clinically staged as dementia at Core Study baseline based on clinical diagnosis
- Change from baseline in NPI-10 and NPI-12
- Proportion of subjects who receive increase and/or initiation of other AD pharmacotherapies

A delayed-start analysis ([Liu-Seifert et al., 2015](#)) will be performed for each efficacy endpoint at various scheduled visits in the Extension Phase. In addition, a mixed effects model for repeated measures (MMRM) will be used to analyze the above endpoints where appropriate.

Biomarker Analyses

The following biomarker endpoints will be summarized by descriptive statistics and graphs:

- Change from baseline in amyloid PET standardized uptake value ratio (SUVR)
- Change from baseline in tau PET signal
- Change from baseline in total hippocampal volume as measured by vMRI
- Change from baseline in the preservation of connectivity as measured by fMRI
- Change from baseline in t-tau, p-tau, A β (1-42) and A β (1-x) in CSF
- Change from baseline A β (1-x) in plasma
- Change from baseline in exploratory biomarkers eg, NFL, VILIP1, YKL-40, and Ng in CSF and plasma

A delayed-start analysis and MMRM model will be used to analyze these biomarker endpoints.

The relationship between efficacy endpoints and biomarker endpoints will be explored using correlation analysis.

Sample Size Rationale

Not applicable.

Table 9 Schedule of Procedures/Assessments in Extension Phase

Phase	Extension												

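### After 4 weeks off drug, unrelated deaths, SAEs and new AEs need not be recorded, so all-cause mortality to Month 24 and the pretreatment AE status of Extension entrants are not assured

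*Protocol*

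**What the plan says.** Section 9.5.4.1 sets the SAE window: "SAEs, regardless of causality assessment, must be collected up to 4 weeks after the last dose of study drug". It makes one exception, for SAEs the investigator judges related to study treatment or a protocol-required procedure; these "should be reported to the sponsor regardless of the length of time that has passed since study completion".

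For AEs, section 9.3.3 says: "New AEs will be collected for 4 weeks post last dose and followed up for 12 weeks, or until resolution, whichever comes first". Section 9.5.1.5.1 agrees and carries procedure-related AEs to the end of participation. Table 5 repeats the limit twice. Note b, on early discontinuers, says "If >4 weeks post last dose, only AEs relating to study procedures will be collected". Note ff, attached to the AE row for all subjects, says "If >4 weeks post last dose, AEs relating to study procedures will be collected only".

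Under section 9.3.3, subjects who stop drug early count as on study "as long as they continue to return for their regularly scheduled clinical assessments at 12 and 24 months". Section 9.7.1.6.1 analyses the primary endpoint regardless of adherence.

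Section 9.5.5 lists the primary reasons for leaving the study as "AE, lost to follow-up, subject choice, withdrawal of consent, pregnancy, study terminated by sponsor, and other", and section 9.7.1.3 repeats the list. The same section says AEs are assessed at the 12- and 24-month visits of discontinuers, with no 4-week limit.

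For Extension safety analyses, Appendix 5 keeps the Core baseline for subjects first randomised to elenbecestat, while "the Extension Phase baseline will be used for subjects who are randomized to placebo but receive elenbecestat during the Extension Phase".

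**The concern.** Two periods lie beyond the 4-week limit yet matter to the analyses.

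The first runs from 4 weeks after an early stop to Month 24. Efficacy is still sought from these subjects. Death is an SAE under section 9.5.1.5.2, so it falls under the 4-week rule. Whether a later death must be reported then turns on an investigator's causality judgement. The death summary in section 9.7.1.8.2 is built from treatment-emergent AEs leading to death, so it can count only what was recorded. Mortality by randomised arm is therefore not assured over the period in which efficacy is followed, and death as a reason for a missing Month 24 CDR-SB may not be identifiable.

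The second runs from 4 weeks after the last Core dose to the first open-label dose. The Extension's primary endpoint is safety, and section 9.7.1.8.2 defines a treatment-emergent event by comparison with the pretreatment state. For former placebo subjects that state is the Extension baseline, and the preceding weeks have no required recording of new unrelated AEs. Table 5 has no medical-history update at Visit 15.

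**Working it through.** The protocol gives no figure of its own here, so the check compares the rules and then sizes the gaps.

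**Rules after week 4 off drug**

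- New AE, unrelated to procedures: not required (9.3.3; 9.5.1.5.1; Table 5 notes b and ff). Section 9.5.5 reads otherwise for discontinuers' 12- and 24-month visits. The two instructions cannot both be followed.
- SAE or death judged unrelated to drug and procedure: not required (9.5.4.1).
- SAE judged related: reportable without time limit (9.5.4.1).
- AE or SAE begun inside the window: AEs followed to 12 weeks or resolution, SAEs to resolution or stabilisation (9.5.1.5.1, 9.5.4.1).
- Vital status: no collection stated.

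**Discontinuers: weeks outside the window up to week 104** = 104 − stop week − 4.

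- Stop at week 26: 74 weeks. Week 52: 48 weeks. Week 78: 22 weeks.

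**Illustrative deaths per arm, both studies pooled.** Inputs: 950 per arm and 30% dropout (9.7.2). Assumptions not in the protocol: all of the 30% stop drug, stopping is even over 24 months (mean 12 months remaining), and annual mortality is 1% (range 0.5% to 2%). Four weeks is 0.92 months.

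- Off-drug subjects: 950 × 0.30 = 285.
- Subject-years beyond 4 weeks: 285 × (12 − 0.92)/12 = 263.
- Share of planned follow-up: 263/(950 × 2) = 263/1,900, about 14%.
- Deaths in that time: 263 × 0.01 = 2.6, against 1,900 × 0.01 = 19 in all. At 0.5%: 1.3. At 2%: 5.3.

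**Sensitivity, Study 301 alone, both arms together.** Let 10% to 30% of 850 subjects (85 to 255) stop drug and stay on study, at week 26 to 78.

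- Low end: 85 × 22/52.18 = 36 person-years; × 0.005 = 0.2 deaths.
- High end: 255 × 74/52.18 = 362 person-years; × 0.02 = 7 deaths.

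**Extension gap.** Inputs: Visit 13 on Day 729 and Visit 15 on Day 813 (Table 5); entry at Visit 15 or within 4 weeks after it (9.1, Appendix 5).

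- Off drug at Visit 15: 813 − 729 = 84 days (12 weeks), or 16 weeks with the latest entry.
- Less the 28-day window: 84 − 28 = 56 days (8 weeks), or 84 days (12 weeks) with the latest entry.
- Chance of at least one AE starting in the gap = 1 − exp(−rate × weeks/52), at an assumed 1 to 2 AEs per subject-year: 14% to 26% over 8 weeks and 21% to 37% over 12 weeks. For its effect on baseline, this applies to former placebo subjects.

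**The case against.** The strongest reply is that the protocol has several other routes for capturing late events, and that the 4-week limit is a deliberate choice applied in several places.

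Much of this stands. Related SAEs have no time limit, and a death from an SAE that began inside the window would be followed. Section 9.5.5 requires subjects who stop attending to be traced for the reason and for AEs. Section 9.4.7 asks for any AE that led to a concomitant medication to be recorded, and states no time limit. Visit 15 is not empty for Extension entrants: physical and dermatologic examination, vital signs, ECG, laboratory tests, full neurologic examination and concomitant medications are all done, and section 9.5.1.5.5 has the subject asked about changes since the last examination.

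So a reader might infer that all events after week 4 are lost. The documents do not support that; the accurate statement is that unrelated ones are not required. A reader might also infer that an off-drug death must be coded as other or lost to follow-up. AE is an available reason, so the coding is merely unspecified. Nor can it be said that deaths will be hidden from the missing-data analyses: section 9.7.1.6.1 leaves those open, and the SAP is not available here.

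It is equally tempting to say that all Extension entrants are affected alike, or that conditions arising off drug will be counted as new on elenbecestat. Appendix 5 keeps the Core baseline for those first given elenbecestat. A condition with a correctly dated onset before the first open-label dose would not be treatment-emergent for former placebo subjects.

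Finally, the file also contains the superseded Amendment 05 text with a 12-week SAE window. That is not a contradiction in the current plan.

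None of these routes is a vital-status check. Tracing covers only subjects who cease to return and names no death item. Examination findings do not give the onset and severity of an event that began weeks earlier.

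**Conclusion.** The point holds in this form. All-cause mortality by randomised arm is not assured to Month 24, because a late death judged unrelated need not be recorded and no vital-status item or death disposition reason is stated. Section 9.5.5 contradicts section 9.3.3 and Table 5 notes b and ff on AE collection at discontinuers' later visits, so sites may record differently. Extension entrants have an 8- to 12-week gap that leaves pretreatment AE status incomplete, chiefly for former placebo subjects and partly mitigated by the Visit 15 assessments.

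The number of deaths at stake is small and uncertain. The 2.6 per arm is an upper bound only on its own inputs: an assumed 1% mortality, even stopping, the whole 30% taken as off drug, and no death captured by another route. The 30% is a sample-size allowance that the protocol does not split into off drug and off study. The gap in the rules does not depend on that figure. The point concerns safety reporting and the interpretation of missing data; it does not change the primary efficacy model.

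**What to change.** (a) For every randomised subject, record vital status, date and cause of death to Month 24/Visit 15 regardless of time since last dose, except where consent to follow-up is withdrawn. Add death to the disposition reasons in sections 9.5.5 and 9.7.1.3, and tabulate all-cause deaths by randomised arm. Reconcile section 9.5.5 with section 9.3.3 and Table 5 notes b and ff on AE collection at the 12- and 24-month visits.

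(b) For Extension entrants, record at Visit 15, or Extension Day 1 if later, all AEs and SAEs with onset since 4 weeks after the last Core dose, and conditions then ongoing. Use this as the pretreatment status for former placebo subjects, and keep the Core baseline in Appendix 5 for those first randomised to elenbecestat.

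The cost is a vital-status eCRF item, a disposition code, an AE review within the existing schedule, and a small extra SAE workload. No procedure is added, and the 4-week window for other events can stay.
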